4.6.4. Vital Signs

The following vital signs parameters will be collected at predose at every in-clinic visit and the unscheduled visit or ET visit:

Protocol: R668-ALG-1702

Date: March 3, 2021

- Respiratory rate (bpm)
- Heart rate (bpm)
- Sitting systolic and diastolic blood pressure (mmHg)
- Body temperature (°C) with the measure method (oral/tympanic/axillary/rectal/temporal)

During the DBPCFC, vital signs will be monitored every 15 to 30 minutes. After initial DBPCFC dose, only pulse and blood pressure need to be taken as part of safety monitoring.

4.6.5. Body Weight and Height

Body height is measured at the screening visit 1. Body weight is measured at the screening visit 1, and every in-clinic visit (except for screening visit 1a).

4.6.6. Physical Examination Variables

The physical examination variable values are dichotomized to normal and abnormal. A thorough and complete physical examination will be performed at screening visits (screening visit 1 and visit 1a), week 12, week 24, week 36 or ET visit. Physical examination is performed at each DBPCFC day.

4.6.7. Spirometry

A spirometer that meets the American Thoracic Society (TS) / European Respiratory Society (ERS) recommendations will be used to measure FEV1 and/or PEFR. During DBPCFC, spirometry should be performed before and after the challenge. FeNO should be done prior to spirometry.

4.7. Pharmacokinetic (PK) Variables

Concentration of functional dupilumab in serum at each time point, obtained prior to dosing, will be considered to be trough values (C_{trough.time point}).

4.8. Anti-Drug Antibody Variable

Anti-drug antibody (ADA) variables include ADA status, titer, NAb status, and timepoint/visit. Samples for ADA assessment will be collected at time points according to Section 10.2. Samples positive in the ADA assay will be further characterized for ADA titers and for the presence of NAb to dupilumab.

Immunogenicity will be characterized by ADA responses and titers observed in patients. The ADA response and titer categories are defined as follows:

• ADA Negative, defined as a negative response in the dupilumab ADA assay at all time points, regardless of any missing samples.

Protocol: R668-ALG-1702

Date: March 3, 2021

- Pre-existing immunoreactivity, defined as either an ADA positive response in the dupilumab ADA assay at baseline with all post first dose ADA results negative, or a positive response at baseline with all post first dose ADA responses less than 4-fold of baseline titer levels.
- Treatment-emergent response, defined as a positive response in the dupilumab ADA assay post first dose when baseline results are negative or missing. The treatment-emergent responses will be further characterized as Persistent, Indeterminate or Transient.
 - Persistent Response: Treatment-emergent ADA positive response with two or more consecutive ADA positive sampling time points, separated by greater than 12-week period (based on nominal sampling time), with no ADA negative samples in between, regardless of any missing samples.
 - Indeterminate Response: Treatment-emergent ADA positive response with only the last collected sample positive in the ADA assay, regardless of any missing samples.
 - Transient Response: Treatment-emergent ADA positive response that is not considered persistent or indeterminate, regardless of any missing samples.
- Treatment-boosted response, defined as a positive response in the dupilumab ADA assay post first dose that is greater than or equal to 4-fold over baseline titer levels, when baseline results are positive
- Maximum Titer Values (Titer value category)
 - Low (titer < 1,000)
 - Moderate $(1,000 \le \text{titer} \le 10,000)$
 - High (titer > 10,000)

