11.4.6. Analysis of Immunogenicity Data

Analysis of ADA will be conducted on samples collected at baseline, week 12, week 24, and week 36. Samples that are positive in the ADA assay will be further characterized for ADA titers and for the presence of an NAb response.

Anti-drug antibody response categories and titer categories that will be assessed are as follows:

- Pre-existing immunoreactivity
- Treatment-emergent response

The treatment-emergent responses will be further characterized as persistent, indeterminate, and transient.

- Treatment-boosted ADA response
- Titer value category (tier range)
 - Low (titer <1,000)
 - Moderate (1,000 ≤ titer ≤ 10,000)
 - High (titer >10,000)
- NAb response in ADA positive patients.

Listings of pre-existing, treatment-boosted, and treatment-emergent ADA responses, ADA titers and NAb positivity presented by patient, time point, and dose group cohort/group will be provided. Incidence of treatment-emergent ADA and NAb will be assessed as absolute occurrence (N) and percent of patients (%), grouped by study cohorts dose group and ADA titer level.

Plots of drug concentrations will be examined and the influence of ADAs and NAb on individual PK profiles may be evaluated. Assessment of impact of ADA and NAb on safety and efficacy may be provided.

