5.9. Analysis of Immunogenicity Data

5.9.1. Analysis of ADA Data

The immunogenicity variables described in Section 4.8 will be summarized using descriptive statistics. Immunogenicity will be characterized by ADA responses and titers observed in patients in the ADA analysis set.

The following will be summarized by treatment group and ADA titer level:

- Number (n) and percent (%) of ADA-negative subjects (pre-existing immunoreactivity or negative in the dupilumab ADA assay at all time points)
- Number (n) and percent (%) of treatment-emergent ADA-positive patients
 - Number (n) and percent (%) of persistent treatment-emergent ADA positive patients
 - Number (n) and percent (%) of indeterminate treatment-emergent ADA positive patients
 - Number (n) and percent (%) of transient treatment-emergent ADA positive patients
- Number (n) and percent (%) of treatment-boosted ADA-positive patients

Listing of all ADA titer levels will be provided for patients with pre-existing, treatment-emergent and treatment-boosted ADA response.

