5.10.2. Immunogenicity and Safety and Efficacy

Potential association between immunogenicity variables and safety may be explored with a primary focus on the following safety events during the TEAE period:

- Injection site reaction (serious or severe and lasting 24 hours or longer)
- Hypersensitivity (SMQ: Hypersensitivity [Narrow])
- Anaphylaxis (SMQ: Anaphylaxis [Narrow])

Potential association between immunogenicity variables and primary efficacy endpoints may be explored (e.g. scatter plot or spaghetti plot).

The safety and efficacy analyses mentioned above will be conducted using the following ADA response categories:

- ADA positive patients, that is patients with treatment-emergent or treatment-boosted response
- ADA negative patients, that is patients with pre-existing immunoreactivity or negative in the ADA assay at all time points
- Patients with persistent treatment-emergent ADA response
- NAb positive patients, that is patients who were positive in the NAb assay at any time point analyzed

• Maximum post-baseline titer level in treatment-emergent or treatment boosted ADA positive patients:

Protocol: R668-ALG-1702

Date: March 3, 2021

- High,
- Moderate,
- Low

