Blood samples for additional exploratory ⁵ research ⁷			X						X						X		X		X

Study Procedure	Scre	ening						Tre	atme	nt Pei	riod					Follo	ow-up	UV	ET
Visit	V1	V1a	V2 Baseline	V3 phone	V4 clinic	V5 phone	V6 clinic	V7 phone	V8 clinic	V9 phone	V10 clinic	V11 phone	V12 clinic	V13 phone	EOT V14 clinic	V15	EOS V16	if app	licable
Day	-57 to -43	-42 to -15	1	15	29	43	57	71	85	99	113	127	141	155	169	211	253		
Week				2	4	6	8	10	12	14	16	18	20	22	24	30	36		
Visit Window (days)				±3	±3	±3	±3	±3	±3	±3	±3	±3	±3	±3	±3	±3	±3		
PK/Drug Concentration and ADA Samples ⁸ :																			
PK/Drug conc. sample			X				X		X						X		X		X
ADA sample			X						X						X		X		X
Genomic DNA sample9:																			
Buccal swab samples for			X																

Date: March 3, 2021

WOCBP = women of childbearing potential

DNA

Footnotes for the Schedule of Events Table

- 1. Study drug will be administered in the clinic on day 1 by the study team, patient's caregiver, or patient. With adequate training, study drug may be administered at home Q2W for the remaining injections. Patient/caregiver will complete an injection log to document compliance with injection of study drug and to document any AEs and concomitant medications.
- 2. During DBPCFC, vital signs will be collected every 15 to 30 minutes. After initial DBPCFC dose, only pulse and blood pressure need to be taken as part of safety monitoring.
- 3. Patients should not take antihistamines within 5 days prior to SPTs and day 1 of the DBPCFCs.
- 4. The food challenges (DBPCFC) will be performed on different days (1 day placebo [oat] protein, 1 day peanut protein, with order determined at random) at least 24 hours, but no more than 7 days, apart and not within 24 hours of a dose of study drug. After the last dose of the DBPCFC, the patient will be monitored for at least 2 hours and then discharged from the clinic.
- 5. Assessments will be performed before the administration of study drug.

Regeneron Pharmaceuticals, Inc. Statistical Analysis Plan

Protocol: R668-ALG-1702 Date: March 3, 2021

- 6. FeNO measurement and spirometry will be performed on the same day, except for visit 1, in which only spirometry is performed. If the DBPCFC is scheduled on the day of the visit, then both FeNO measurement and spirometry will be performed twice before the patient goes home: once before DBPCFC, once after DBPCFC. FeNO should be done prior to spirometry.

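### The persistent ADA definition needs positives more than 12 weeks apart, but samples are exactly 12 weeks apart, so a patient positive at weeks 24 and 36 only is labelled transient

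*SAP*

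**What the plan says.** SAP 4.8 divides treatment-emergent ADA responses (baseline negative or missing, positive after the first dose) into three classes.

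- **Persistent:** "two or more consecutive ADA positive sampling time points, separated by greater than 12-week period (based on nominal sampling time"), with no negative sample between the positives and missing samples ignored.
- **Indeterminate:** "Treatment-emergent ADA positive response with only the last collected sample positive in the ADA assay".
- **Transient:** "Treatment-emergent ADA positive response that is not considered persistent or indeterminate, regardless of any missing samples". This is the residual class.

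On timing, Protocol 11.4.6 states: "Analysis of ADA will be conducted on samples collected at baseline, week 12, week 24, and week 36". The schedule in SAP 10.2, under "PK/Drug Concentration and ADA Samples", agrees: days 1, 85, 169 and 253, plus an early termination (ET) sample. Protocol 11.4.6 names the three classes without defining them, so SAP 4.8 is the only definition.

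SAP 5.9.1 commits to a table of the three classes, including "Number (n) and percent (%) of transient treatment-emergent ADA positive patients". SAP 5.10.2 uses one of them, "Patients with persistent treatment-emergent ADA response", as a category in optional association analyses.

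**The concern.** The limit is strict, it is applied to nominal time, and it equals the sampling interval. Two neighbouring scheduled positives can therefore never satisfy it, and the ±3-day visit window makes no difference.

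The patient most clearly affected first turns positive at week 24 and is positive again at week 36. Protocol 6.1 puts the last dose at week 22, so this patient is still positive 14 weeks after dosing ended, on every sample since the response appeared. The table would nevertheless call the response transient.

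The rule is also out of order with itself. A patient positive only at week 36 is indeterminate. Adding a positive at week 24 gives more evidence of persistence, yet moves the patient to transient.

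What is at stake is the descriptive split in SAP 5.9.1 and one category in SAP 5.10.2. With about 24 patients planned (Protocol 7.1), one or two patients could make up a whole row of that table.

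**Working it through.** The plan gives no figure to reproduce here. The check classifies every possible result sequence by the rule as written.

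**Nominal gaps** (days from SAP 10.2)

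- Week 12 to 24: 169 − 85 = 84 days; 84/7 = 12.0 weeks.
- Week 24 to 36: 253 − 169 = 84 days; 84/7 = 12.0 weeks.
- Week 12 to 36: 253 − 85 = 168 days; 168/7 = 24.0 weeks.

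**Enumeration.** Each of weeks 12, 24 and 36 is positive (+), negative (−) or missing (m), which gives 3³ = 27 sequences. Of these, 2³ = 8 have no positive, leaving 27 − 8 = 19. Baseline is negative or missing. The separation is read as the span from first to last positive of a run with no negative inside it.

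| Class as written (more than 12) | Sequences (weeks 12, 24, 36) | Count |
|---|---|---|
| Persistent | (+,+,+), (+,m,+) | 2 |
| Indeterminate | (−,−,+), (−,m,+), (m,−,+), (m,m,+), (−,+,m), (m,+,m), (+,m,m) | 7 |
| Transient | (−,+,+), (m,+,+), (+,+,m), (+,+,−), (+,−,+), (+,−,−), (+,−,m), (+,m,−), (−,+,−), (m,+,−) | 10 |

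**Effect of at least 12.** Four sequences have a run spanning exactly 12 weeks and move from transient to persistent: (−,+,+), (m,+,+), (+,+,m) and (+,+,−).

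| Sequences | Limit | Persistent | Indeterminate | Transient |
|---|---|---|---|---|
| All 19 | more than 12 | 2 | 7 | 10 |
| All 19 | at least 12 | 6 | 7 | 6 |
| 7 with complete samples | more than 12 | 1 | 1 | 5 |
| 7 with complete samples | at least 12 | 3 | 1 | 3 |

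**Transient but positive at the last collected sample.** As written there are 4 of 19: (−,+,+), (m,+,+), (+,+,m) and (+,−,+). With at least 12, only (+,−,+) remains, and its label comes from the negative in between, not from the limit.

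**The other reading.** If the separation means the gap between adjacent positives, the rule as written makes even (+,+,+) transient. Only (+,m,+) is then persistent, and the counts are 1/7/11.

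**ET samples.** ADA is sampled at ET, and Protocol 9.1.2 asks patients withdrawn after week 24 to return for it. So (+,+,m) is transient only if no later ET sample exists. Assume the SAP 6.5 windows supply the nominal week (days 177–232 as week 30, day 233 onward as week 36):

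- Weeks 12 and 24 positive, ET positive: span 30 − 12 = 18 or 36 − 12 = 24 weeks; persistent under both limits.
- Week 24 and ET at week 30 positive, week 12 negative or missing: span 6 weeks; transient under both.
- Week 12 and ET at weeks 14 to 22 positive: span 2 to 10 weeks; transient under both.
- Week 12 and ET mapped to week 24 positive: span 12 weeks; moves from transient to persistent.

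The sum of the three classes is 19 under either limit, so treatment-emergent incidence changes by 0.

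**The case against.** The best defence is that this is a choice of definition, not a contradiction. The three classes cover every case without overlap and can be programmed. Transient is openly the residual class, and nothing in either document says that two positives exactly 12 weeks apart were meant to count as persistent. Read first to last, the strict limit demands positives at weeks 12 and 36 with no negative at week 24. That is a coherent, if stringent, standard. On this schedule, at least 12 would make any two neighbouring scheduled positives persistent, so the duration test would no longer screen out any scheduled run of two.

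The remedy also has a cost: (+,+,−), negative at the last sample, becomes persistent, although its present transient label is defensible. With complete samples, only one sequence that is positive at the last visit changes, (−,+,+), 1 of 7.

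Finally, the patient-level data will be visible. SAP 5.9.1 plans this: "Listing of all ADA titer levels will be provided for patients with pre-existing, treatment-emergent" and treatment-boosted responses. Protocol 11.4.6 plans listings by patient and time point. In a trial this small a reader could reclassify by hand.

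These points limit the size of the problem, and the side effect on (+,+,−) is real. They do not repair the label. A stricter standard for persistence could be defended, but it does not justify calling a response transient when no later sample has shown it to end. Nor does it explain why (−,−,+) is indeterminate and (−,+,+) is not. The listings would contradict the table rather than correct it.

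**Conclusion.** The rule is wrong as written, at minor severity. Patients with (−,+,+) or (m,+,+) will be tabulated as transient while positive at their last two samples, and no other text in the protocol or SAP overrides this. (+,+,m) has the same fate when no later ET sample exists.

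The damage is confined to the descriptive persistent/transient split and an optional exploratory category. The secondary objective, treatment-emergent ADA incidence, is untouched, and so is efficacy.

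The conclusion for (−,+,+) and (m,+,+) holds on either reading of the separation and does not depend on ET samples. The counts 2/7/10 and 6/7/6 assume the first-to-last reading. The ET results assume that the SAP 6.5 windows apply to ADA, which that section's examples of by-visit data do not name. The documents give no ADA rates, so the number of patients affected is unknown.

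**What to change.** Before database lock, make two changes.

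1. In SAP 4.8, require the positives to be separated by at least 12 weeks of nominal time, measured from the first to the last positive of the run. This also settles the first-to-last versus adjacent-gap question.
2. Footnote the SAP 5.9.1 table with the number of patients classed as transient whose last collected sample, including any ET sample, is positive. The new limit alone does not cover the ET cases with spans under 12 weeks. The footnote will also count (+,−,+), so it should give the sequences.

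The cost is one phrase and one footnote, with no new data; the SAP overview already allows revision before lock. The downsides are that (+,+,−) becomes persistent and that the wording may differ from a definition used in other studies. If the strict limit must be kept for that reason, state the first-to-last reading and rely on the footnote alone. Either way, the decision should be made before the ADA results are seen.

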4.9. Pharmacodynamic and Biomarker Variables

Pharmacodynamic and biomarker variables are:

- Serum TARC and total IgE
- Peanut-specific IgE, IgG, IgG4
- Titrated Skin Prick Test
- Fractional Exhaled Nitric Oxide (FeNO)
- Basophil sensitivity to peanut allergen (EC50)
- Frequency of peanut specific Th2A cells

Biomarker samples will be collected at time points according to according to Section 10.2.

Protocol: R668-ALG-1702

Date: March 3, 2021

5. STATISTICAL METHODS

For continuous variables, descriptive statistics will include the following: the number of patients reflected in the calculation (n), mean, standard deviation, median, first quartile (Q1), third quartile (Q3), minimum, and maximum.

Protocol: R668-ALG-1702

Date: March 3, 2021

For categorical or ordinal data, frequencies and percentages will be displayed for each category.

5.1. Demographics and Baseline Characteristics

Demographics and baseline characteristics will be summarized for SAF. Listing of demographics and baseline characteristics will be presented.

5.2. Medical History

Medical history will be summarized by primary SOC and PT based on SAF. The table will be sorted by decreasing frequency of SOC followed by PT based on the overall incidence. Medical history will be listed based on the SAF.

Subject allergic/atopic medical history and subject family allergic/atopic medical history will be summarized and listed.

5.3. Prior and Concomitant Medications/Procedures

Number and proportion of patients taking prior/concomitant medications, prohibited medications and rescue medications will be summarized for study total based on the SAF by ATC level 2 and ATC level 4, sorted by decreasing frequency of ATC level 2 and ATC level 4 based on the overall incidence. Patients will be counted only once for each medication class (ATC levels 2 and 4) linked to the medication.

Number and proportion of patients taking prior/concomitant procedures will be summarized for study total based on the SAF, sorted by decreasing frequency of SOC and PT based on the overall incidence. Patients will be counted only once for each SOC and PT linked to the procedure.

In addition, the summary of prior/concomitant medications/procedures will be performed for patients who were impacted by COVID-19 pandemic and not impacted by COVID-19 pandemic, respectively. The summary will be performed for pre-, during, and post-COVID-19 periods for patients impacted by COVID-19 pandemic, if applicable.

Number and proportion of patients taking at least one epinephrine for treatment of acute-allergic reactions will be summarized during the following periods,

- Screening DBPCFCs of peanut protein
- Week 24 DBPCFCs of peanut protein
- Week 36 DBPCFCs of peanut protein

Kaplan-Meier curves for time to first rescue treatment use will be created.

Listing of pre-treatment and concomitant medications will include generic name, ATC levels 2 and 4, indication, the study day of onset (for medications started before treatment, the study day of onset = date of medication start – date of the first dose; for medication started on or after treatment, the study day of onset = date of medication start – date of the first dose + 1), the study day of medication end date, ongoing status, dose, frequency, and route.

Protocol: R668-ALG-1702

Date: March 3, 2021

5.4. Patient Disposition

The following summaries will be provided:

- The total number of screened patients and the screen failure reasons including screen failure at visit 1 and visit 1a
- The total number of enrolled patients
- The total number of patients in each analysis set
- The total number of patients who discontinued the study and the reasons for discontinuation (including COVID-19 related reasons)
- The total number of patients who discontinued the study treatment permanently and the reasons for discontinuation (including COVID-19 related reasons)

The following listings will be provided:

- Listing of patients disposition including: date of enrollment, date of first study drug injection, date of the last visit, completed study or discontinued by reason
- Listing of patients enrolled but not treated, and treated but not enrolled
- Listing of patients prematurely discontinued from the study or study treatment, along with reasons for discontinuation
- A listing of protocol deviations will be provided

Kaplan-Meier curve for time to withdraw from the study and from the study treatment will be created, respectively.

5.5. Extent of Study Treatment Exposure and Compliance

5.5.1. Measurement of Compliance

The compliance with study treatment will be calculated as follows:

Treatment Compliance of study drug = (Number of study drug injections during exposure period)/(Number of planned study drug injections during exposure period) x 100%

Protocol: R668-ALG-1702

Date: March 3, 2021

where temporary dose discontinuation is ignored.

Loading doses for the same patient will be counted as 1.

Summary of study drug administration will include the number of study drug doses administered and treatment compliance. The treatment compliance will be presented by the following specific ranges: <80%, and $\ge80\%$.

Listing of study drug compliance will be presented with study drug, study drug injection date/time, study day, injection location, kit number, whether or not the total dose is administered for each dose, and compliance rate.

5.5.2. Exposure to Investigational Product

The duration of treatment exposure during the study in day will be presented and is calculated as:

(Date of last study drug injection – date of first study drug injection) + 14 days

Note: the calculations are regardless of temporary dosing interruption.

Summary of exposure to study drug will include the number of study drug administered and duration of exposure. The duration of exposure during the study will be summarized using number of patients, mean, SD, median, Q1, Q3, minimum and maximum.

In addition, the duration of exposure to study drug will be summarized categorically by counts and percentages for each of the following categories as well:

```
\geq14 days, \geq28 days, \geq42 days, \geq56 days, \geq70 days, \geq84 days, \geq98 days, \geq112 days, \geq126 days, \geq140 days, \geq154 days, and \geq168 days
```

The duration of observation period during the study in day is calculated as:

(Date of last visit – date of first study drug injection) + 1 day

The duration of observation period will be summarized descriptively using number of patients, mean, SD, median, Q1, Q3, minimum and maximum. In addition, the number (%) of patients with observation periods will be presented by specific time periods. The time periods of interest are specified as:

```
<15 days, \geq15 days, \geq29 days, \geq43 days, \geq57 days, \geq71 days, \geq85 days, \geq99 days, \geq113 days, \geq127 days, \geq141 days, \geq155 days, and \geq169 days
```

Listing of dose administration will be presented with information on administration date/time, study day, locations of injections, kit number, and whether or not the total dose is administered for each dose will be presented.

